#### Experimental design:

MRS and MRE for liver fat and fibrosis will be done if not done previously following enrollment into study. For flexibility of scanning we will allow subjects to undergo MR scans at any time prior to the screening visit. A standard 75 gm labeled (6,6-H2 glucose) OGTT will be performed over 240 mins to determine glucose tolerance status. OGTT: The labeled OGTT will enable us to concurrently measure various indices of insulin action, insulin secretion, and DI (composite measure of insulin secretion accounting for the prevailing level of IR). Furthermore, this protocol also allows measurement of EGP; this method was validated (41; 67-73) in various population cohorts in the US and Europe. OGTT will not be performed on subjects taking insulin for management of hyperglycemia. Subjects will be required to fast overnight and report to the CRTU at Mayo Clinic or UVa campus on the morning of testing. Only sips of water will be allowed until testing is complete. An 18-gauge cannula will be inserted in a forearm for blood withdrawal. After baseline sampling (-15 and 0 minutes), a dextrose solution (Limeondex [Fisher]) will be consumed within a few minutes; this solution will contain 3 g of 6,6- H2] glucose (~4% enrichment) in 72 g of dextrose. Blood samples will be withdrawn at 10, 20, 30, 60, 90, 120, 150, 180, 210, and 240 minutes for measurement of glucose, insulin, C-peptide, glucagon, and [6,6-H2] glucose enrichment. At the end of the study, subjects will be provided a snack and dismissed.

#### Cortisol study:

Subjects will return on a different day for the in-patient visit. Subjects will be admitted to the CRTU between 4 pm and 6 pm on the evening before the study and will be provided a standard supper (carbohydrate: protein: fat in the ratio of 50:20:30). consisting of ~33% of the subject's total estimated calorie intake based on Harris Benedict + 20% calorie requirements. Urine pregnancy test will be done in women of child bearing potential. Subjects will be awakened the following morning and a catheter will be placed in a forearm vein for tracer infusion and in the dorsum of the opposite hand which will be placed in a heated box (~55°C) to permit sampling of arterialized venous blood. A bladder catheter will be offered on the morning of study if subjects are unable to use a bedpan, urinal or bedside commode. A primed (24µCi) continuous (0.24 µCi/min) infusion of [1,2,6,7–H] cortisol will

be started at minus 120 minutes and blood will be collected for measurement of [H] cortisol concentration at timed intervals in each subject to calculate basal production rate of cortisol. At time 0, subjects will ingest 1.0 mg of [4-C] cortisone and 1.0 mg of [9,12,12-H3] cortisol. At time 0, the [H] cortisol infusion rate will be increased in order to mimic the temporal pattern of change as previously published (23). Arterialized venous blood then will be sampled at periodic intervals (suggested timelines are -30, 0, 20, 40, 60, 75, 90, 120, 150, 180, 210, 240 minutes) for measurement of [H] cortisol, [H] cortisone, [C] cortisone and [C] cortisol enrichment, and [H] cortisol [H] cortisone specific activity (23). At UVa subjects will come in to CRU morning of study and all other interventions will be similar as outlined above.

#### Analytical methods

All blood samples will be immediately placed on ice, centrifuged at 4oC, separated and stored at -80oC until analyses. Plasma glucose will be analyzed using YSI (yellow springs Ohio), plasma insulin will be measured using a chemiluminescence method with the Access Ultrasensitive Immunoenzymatic assay system (Beckman, Chaska, MN) and C-peptide and glucagon measured using a radioimmunoassay; Linco Research. Plasma [6,6-H2] glucose enrichment will be measured using gas chromatographic mass spectrometry (74). Plasma cortisol, cortisone, D3 cortisol, D3 cortisone, 13C cortisone and C13 cortisol enrichments will be measured using liquid chromatography tandem mass spectrometry as previously described (23; 75; 76). [H] cortisol radioactivity will be measured using high performance liquid chromatography followed by liquid scintillation counting (23; 77). Body composition will be measured using Lunar dual energy X-ray absorptiometry software (GE Healthcare Technologies).

#### **Calculations:**

[H] cortisol will be used to trace the systemic rate of appearance of both [C] cortisol and [H] cortisol. Thus, the systemic rate of appearance (ug/min) of [C] cortisol derived from the ingested [C] cortisone will be calculated by using Steele's steady state equation. Hepatic [C] cortisol production will be calculated as the area under the curve for the rate of appearance of [C] cortisol divided by one minus the hepatic extraction of [H] cortisol (23; 78). Insulin sensitivity and secretion indices will be calculated using unlabeled and labeled models established by us previously (41; 61-67)

#### **Statistical Analysis**

Demographics and baseline characteristics will be described by treatment group and the groups compared using two-sample t-tests.

#### **Primary analysis**

We will first compare the change in LFF from baseline (time 0) to post treatment (12 week) between the two treatment groups, one with patients treated with active drug and the other with patients treated with placebo, using analysis of covariance (ANCOVA) including baseline LFF as a covariate. This primary analysis will be based upon the intention to treat principle, including all patients randomized who have both baseline and post treatment measures of LFF.

Next we will compare rates of hepatic conversion of [C] cortisone to [C] cortisol between the groups, again using ANCOVA, analogous to the analysis of LFF.

#### **Power for Primary Analysis**

A sample size of 45 in each group will have 80% power to detect a difference in means of 3.1 assuming a mean square error (MSE) of 4.6 using an ANCOVA and a two-sided test with alpha 0.05. The MSE of 4.6 is estimated based upon the study of Stefan et al. (28) where an MSE of 4.6 and a difference in group means of 2.6 were observed. We anticipate that as many as 5 patients could drop out of each treatment group and so will recruit additional patients to each treatment group for a total of 100 patients. Based upon this our study is adequately sized to achieve our aims. We will now also include subjects with fibrosis score 0 up but with liver fat % >5 % as we believe data from these subjects will also be valuable and of interest in the final analyses. Since fibrosis scores are unlikely to change in the short duration of this trial and change in fibrosis is a secondary endpoint we believe this approach does not distract from our primary endpoint related to lowering of liver fat %.

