That the liver is an important regulator of the diabetogenic effects induced by GC use is borne by the fact that liver selective GC receptor antagonists have been shown to reduce fasting glucose and improve hepatic insulin action during a hyperinsulinemic euglycemic clamp (27). A recent clinical trial has shown that 11 $\beta$ -HSD inhibition for 12 weeks can reduce liver fat (~14%), and total body weight without any effects on insulin induced suppression of glucose production (28). However, to our knowledge liver specific inhibitors of 11 $\beta$ -HSD have not been rigorously tested in the manner we currently propose.

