Currently, the favored technique for estimating the liver fat fraction (LFF) is guantitative magnetic resonance (MR) imaging (32). MR imaging in general ignores the multispectral nature of hepatic TG that can be used to distinguish between saturated fat, monounsaturated fatty acid (MUFA), and polyunsaturated fatty acid (PUFA). MR spectroscopy (MRS) of liver fat has been performed, and although it suffers from sampling error due to the small voxel size relative to liver size, the wealth of spectral information obtained can be used to determine the composition and quantity of hepatic fatty acids. Previous MRS studies of the liver (32-37) have used manual fitting techniques that are time intensive and operator biased (38-43). LC Model is a semi-automated, widely available MRS fitting program that can quantify up to 10 different fat resonances in the liver (38). We have developed a reliable, reproducible method for acquiring liver spectra on a 3T MRI scanner to calculate liver fat composition. This method was evaluated with 6 nondiabetic subjects scanned during 2 separate sessions, 10 days apart. In each session, 4 separate liver fat measurements were taken (8 scans/subject). Spectra were preprocessed (phased, averaged) and then analyzed using LC Model software. Quantified spectral data were combined into 4 liver fat indices: total fatty acids (TFA), polyunsaturated fatty acid index (PUFAI), total unsaturated fatty acids (TUFA), and the standard fat water ratio (FWR), similar to the LFF. Calculations were performed to evaluate intraclass correlation coefficient (ICC) for each index and variability within the cohort (ie, intrascan, interscan, inter-session, intersubject). The FWR varied from 0.02 to 0.26, indicating a wide range of liver fat in this healthy cohort (normal was defined as FWR≤0.05). Liver fat index ICCs for intrascan, interscan, and intersession reliability ranged from 0.92 (PUFAI interscan) to 0.99 (FWR intrascan and interscan), indicating that our method is highly reproducible. Variance components models (SAS PROC NESTED) showed that the majority of variance in the indices resulted from differences between subjects (FWR=98%, TFA=90%, TUFA=96%, PUFAI=89%). TFA had a small intersession variance (4%), whereas TFA and PUFAI had small scanner-related variance (6% and 9%, respectively). The remaining variance components were negligible (39). Mayo Clinic is implementing this scanning method for patients being evaluated for liver fat. We recently concluded a nutritional intervention trial in which this method was used to measure hepatic fat in subjects with IFG (impaired fasting glucose) (40; 41).

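### The stated 80% power for a difference of 3.1 does not follow from the plan's own inputs, whether the 4.6 is a variance or a residual SD

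*Combined protocol and SAP*

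**What the plan says.** The section Power for Primary Analysis holds the plan's only power calculation. It says that 45 per group "will have 80% power to detect a difference in means of 3.1 assuming a mean square error (MSE) of 4.6 using an ANCOVA", at two-sided alpha 0.05. It takes the 4.6 from an earlier trial of an 11β-HSD1 inhibitor, "where an MSE of 4.6 and a difference in group means of 2.6 were observed". It then allows for attrition ("We anticipate that as many as 5 patients could drop out of each treatment group"), arrives at 100 patients in all, and concludes: "Based upon this our study is adequately sized to achieve our aims". The Treatment paragraph likewise describes 50 per group, with about 5 dropouts in each, as enough for the primary hypotheses.

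The Primary analysis section specifies an ANCOVA of change in liver fat fraction with baseline as covariate, "including all patients randomized who have both baseline and post treatment measures of LFF". Dropouts without a second scan therefore reduce the analysed number.

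The power paragraph attaches no units to 3.1, 2.6 or 4.6. It later refers to "our primary endpoint related to lowering of liver fat" as a percentage.

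**The concern.** A power statement for a two-group ANCOVA links five quantities: number per group, alpha, difference, residual SD and power. Any four fix the fifth. Here all five appear to be given, and they disagree.

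The label on the 4.6 adds to the difficulty. A mean square error is a variance, so the residual SD would be √4.6 = 2.145. The same name is sometimes used loosely for the root mean square error, in which case the residual SD is 4.6. The two readings differ by a factor of more than two on the SD scale, and the plan does not say which is meant.

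The claim of adequate size and the total of 100 rest on this one sentence. As it stands, a reader cannot establish what difference the trial can detect, or whether power reaches 80% at the 2.6 quoted beside the calculation.

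**Working it through.** **Inputs, all from Power for Primary Analysis.** n = 45 per group evaluable (50 recruited), two-sided alpha 0.05, target difference 3.1, difference observed in the cited trial 2.6, and the figure 4.6. The test is the ANCOVA of the Primary analysis section, with one covariate.

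**Method.** The standard error of the adjusted difference is SE = σ√(2/n), where σ is the residual SD. The noncentrality is δ/SE. Power comes from the noncentral t with 2n − 3 = 87 degrees of freedom (critical value 1.988). The small loss of precision from chance imbalance in the covariate is ignored.

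**Attempt to reproduce the stated 80% for 3.1**

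- *4.6 as a variance.* σ = 2.145, SE = 2.145 × √(2/45) = 0.452, noncentrality 3.1/0.452 = 6.86. Power is above 99.9%.
- *4.6 as a residual SD.* SE = 4.6 × √(2/45) = 0.970, noncentrality 3.1/0.970 = 3.20. Power is 88.5% (89.2% by the normal approximation).

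Neither gives 80%. Solving for the SD that would give 80% at 3.1 with n = 45 yields σ = 5.19, a variance of 26.9. Neither figure appears in the documents.

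**What the inputs do give**

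| | 4.6 is a variance | 4.6 is a residual SD |
|---|---|---|
| Power for 3.1, n = 45 | >99.9% | 88.5% |
| Power for 2.6, n = 45 | >99.9% | 75.5% |
| Difference detectable with 80% power, n = 45 | 1.28 | 2.75 |
| n per group for 80% power at 3.1 | 9 | 36 |
| n per group for 80% power at 2.6 | 12 | 51 |

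**Effect of dropout on the SD reading.** Power for 2.6 at 45, 46, 47, 48, 49 and 50 evaluable per group is 75.5, 76.5, 77.4, 78.2, 79.1 and 79.9%. At 50 per group, the difference detectable with 80% power is 2.60 and power for 3.1 is 91.6%.

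**Could one misstated input explain the sentence?** Three candidates come close, all with 4.6 as an SD. Each departs from the text.

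- *90% power instead of 80%.* By the normal approximation, (1.960 + 1.282) × 4.6 × √(2/45) = 3.14, which rounds to 3.1. By the t calculation it is 3.18.
- *Alpha 0.025 instead of 0.05.* The detectable difference is 3.03, and power for 3.1 is 81.8%. The plan states 0.05 and mentions no split.
- *4.6 as the raw SD at each visit, analysed as simple change.* This gives 80% only at a baseline correlation of about 0.36, which the plan does not state. ANCOVA at that correlation would give about 92%.

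**Attrition.** 45/(1 − 0.10) = 50 per group, 100 in total. This step is consistent.

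**The case against.** The strongest reply is that the error is conservative. The plan claims power only for 3.1, and power for 3.1 exceeds 80% on both readings. The 2.6 is reported as another trial's result, not adopted as a target, and on the SD reading the shortfall there is 4.5 percentage points at most and about 0.1 point if all 50 per group are evaluable. All of this is correct, and it is why the point calls for a correction of wording and not a larger trial. It does not make the sentence right. The 2.6 is also the only observed effect given in the calculation, and no reason is offered for aiming at something larger.

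A second reply is that 80% may simply be a slip for 90%, since the normal approximation then gives 3.14. That is plausible, and if it is confirmed the repair is one number. It remains inference: it presupposes the SD reading, and the documents do not confirm it.

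A third is that the variance reading is unrealistic, because it would need only 9 per group. I agree that the SD reading is likelier. Still, the plan uses the name of a variance twice, and the source is not available here.

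On units, percentage points is the natural reading of the power paragraph. The ratio scale in the Hepatic fat section ("The FWR varied from 0.02 to 0.26") comes from a reproducibility study. The reduction of about 14% cited in the background may be a relative or within-group figure, so it need not conflict with 2.6. These are reasons to state the units; the arithmetic does not depend on them.

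**Conclusion.** The concern holds. With the stated inputs, the figure of 80% for 3.1 is wrong on either reading of 4.6, and the gap (88.5% or above 99.9%) is well beyond rounding or choice of method. The difference detectable with 80% power is 2.75 or 1.28, not 3.1.

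The consequence is bounded. The trial is not shown to be underpowered for its stated target. Power below 80% arises only at 2.6 and only if 4.6 is an SD. In that case the claim of adequate size needs qualifying; on the variance reading it does not.

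The results assume equal groups, a single baseline covariate and a residual SD that carries over unchanged from the cited trial. This should be fixed, because it is an error in the only calculation supporting the sample size.

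**What to change.** Check the source of the 4.6, state whether it is a variance or a residual SD, and give units for 4.6, 3.1 and 2.6. Then replace the power sentence with whichever of these applies:

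- *If a residual SD:* With 45 evaluable per group, power is 80% for a difference of 2.75, 88.5% for 3.1, and 75.5% for the 2.6 seen in the cited trial (79.9% if all 50 per group are evaluable).
- *If a variance:* With 45 evaluable per group, power is 80% for a difference of 1.28 and above 99.9% for 2.6 and 3.1.
- *If another input was misstated* (power, alpha or an assumed correlation): correct that input and recompute.

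In every case, say why 3.1 rather than 2.6 is the target. If the SD reading is confirmed, qualify the statement that the study is adequately sized.

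The cost is one check of the sponsor's source and a wording change in the protocol and SAP. The number of patients and the analysis stay as they are. The only drawback is that, on the SD reading, the plan would show power slightly below 80% at the effect it cites.

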#### **Secondary Analysis**

The data for the primary outcomes will be explored estimating treatment effects by sex. These too will be tested in the ANCOVA, including interaction terms between treatment and sex. Outcomes related to secondary hypotheses will be analyzed analogously to the primary outcomes, using ANCOVA.

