#### Approach:

We propose to combine the triple tracer cortisol technique with voxel matched MRS and MRE liver (pre vs. post) to evaluate hepatic cortisol production and hepatic fat and hepatic fibrosis. We will conduct baseline testing in subjects to estimate baseline hepatic cortisone to cortisol conversion. We will also establish glucose tolerance status by our established labeled OGTT ( $6,6^{2}H_{2}$  glucose). Following baseline evaluation subjects with NASH, NAFLD, will be randomized to one of two groups and treated either with active drug (liver specific 11 $\beta$ -HSD type 1 inhibitor) or placebo for 12 weeks +/- 1 week. OGTT, liver MRS, MRE and triple tracer cortisol study will be repeated. Liver enzymes (AST, ALT, ALP) as well as other safety tests (CPK,TSH,INR,T bilirubin) will be measured before, monthly during therapy and at one month following therapy. Details in the DSMP.

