#### II) Secondary Hypotheses:

a) Liver enzymes (AST, ALT) will be reduced in subjects treated with AZD4017 as compared to placebo.

- **b)** Liver fibrosis measured with MRE will be reduced in subjects treated with AZD4017 as compared to placebo.
- c) Total insulin sensitivity (Si) and hepatic insulin sensitivity (Si liver) will be improved after treatment with AZD4017 than at baseline.
- **d)** Total insulin sensitivity (Si) and hepatic insulin sensitivity (Si liver) will be improved in subjects treated with AZD4017 as compared to placebo.

**Exploratory Aim (future plan):** We wish to analyze biomarkers of fibrosis and 11  $\beta$  HSD polymorphisms since polymorphisms in the 11 $\beta$ -HSD1 gene are also associated with components of the metabolic syndrome (59; 60). We wish to test if polymorphisms are likely associated with who may or may not respond to the 11  $\beta$  HSD inhibitor.

**Biomarkers: NAFLD, NASH and Inflammation**: NAFLD and NASH are increasing in incidence and prevalence in the United States and worldwide, in parallel with the increasing rates of obesity (61).

Both disorders are characterized by the presence of hepatic steatosis. NASH is distinguished from NAFLD on the basis of liver injury and liver inflammation (62). One disease pathogenesis paradigm holds hepatocyte cell death via lipoapoptotic pathways as a central event in the onset of progressive forms of NASH; furthermore, hepatocyte apoptosis correlates with fibrosis stage in NASH patients (63; 64). There are many circulating surrogate

markers for fibrosis in NASH. The enhanced liver fibrosis (ELF) score is a function of serum levels of hyaluronic acid (HA), tissue inhibitor of metalloproteinases-1 (TIMP-1), and procollagen III N-terminal peptide (PIIINP) is a validated tool for assessing serum fibrosis (65). Other clinical surrogates include the AST/platelet ratio index (APRI) and age-spleen-platelet ratio index (ASPRI); however, the ELF test is unique in its incorporation of three molecules involved in the synthesis and breakdown of extracellular matrix. Newer serum based scores such as APRI (AST to platelet ratio index), FIB-4 (Age, ALT,AST, platelet count), NAFLD fibrosis score (age,ALT,AST,platelet count,BMI,albumin, impaired fasting glucose/diabetes) and BARD (ALT/AST ratio,BMI,diabetes) score may be calculated using the data gathered. In this study we will be able to correlate MRE results with circulating levels of all proposed biomarkers.

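### AST and ALT are scheduled monthly, but the plan's ANCOVA uses only baseline and week 12, so patients without a week-12 value leave the liver-enzyme test and their earlier readings go unused

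*Combined protocol and SAP*

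**What the plan says.** The between-group enzyme hypothesis is item (a) under Secondary Hypotheses: "Liver enzymes (AST, ALT) will be reduced in subjects treated with AZD4017 as compared to placebo". The Approach section sets the schedule. "Liver enzymes (AST, ALT, ALP) as well as other safety tests" "will be measured before, monthly during therapy and at one month following therapy".

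The Secondary Analysis section gives one rule for all such outcomes: "Outcomes related to secondary hypotheses will be analyzed analogously to the primary outcomes, using ANCOVA". The template it points to, under Primary analysis, compares change from baseline to week 12 with baseline as covariate. It invokes intention to treat, with the analysis set defined as "including all patients randomized who have both baseline and post treatment measures of LFF".

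On attrition, Power for Primary Analysis says: "We anticipate that as many as 5 patients could drop out of each treatment group". Recruitment is set accordingly, "for a total of 100 patients".

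The documents contain no repeated-measures model, imputation rule or missing-data sensitivity analysis. Safety detail is deferred to a separate data and safety monitoring plan (DSMP), which is not among them.

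**The concern.** For liver fat, MRE and the OGTT, a two-point ANCOVA uses everything the schedule provides, because Study testing places them at screening and three months only. AST and ALT are different: they have stated on-treatment readings between baseline and week 12. Under the two-point rule, a patient who leaves after month 2 contributes nothing to the enzyme test, although two post-baseline values are on file.

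This matters because the enzymes also belong to the monthly safety panel, so the outcome itself could influence who stays. If it does, patients with a week-12 value are a selected group, and the intermediate readings are what could correct for that selection. At stake is the estimate for one named secondary hypothesis. The primary liver-fat result is not affected.

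**Working it through.** **1. The plan's own dropout figures.** 45 evaluable per arm with 10% loss gives 45 / (1 − 0.10) = 50 per arm and 2 × 50 = 100 in total, which reproduces. Expected losses are at most 2 × 5 = 10 of 100. The plan gives no power or precision figure for AST or ALT.

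**2. Schedule against analysis.**

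| Outcome | Scheduled values | Used by the two-point ANCOVA |
|---|---|---|
| Liver fat, MRE, OGTT | baseline, 3 months | all |
| AST, ALT | baseline, monthly on therapy (about months 1, 2, 3), one month after | baseline and week 12 |

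**3. Size, by simulation.** The documents give no enzyme means, SDs or correlations, so these inputs are assumed: 50 per arm, ALT SD 25 U/L, between-visit correlation 0.6 to 0.8 (exchangeable and AR(1)), about 10% without a week-12 value, 3,000 runs. Complete-case ANCOVA is compared with a regression estimator that uses baseline, month 1 and month 2, standing in for a mixed model. Negative values favour the drug.

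| Who leaves | True difference | Complete-case ANCOVA | All visits |
|---|---|---|---|
| Active: 5 of 50 with largest month-2 rise; placebo: at random | 0 | −1.2 to −2.8 | within 0.1 of 0 |
| Largest month-2 rises, whichever arm | −8 | −6.9 to −7.6 | −7.9 to −8.1 |
| At random | any | almost no difference between methods | SE gain about 1% |

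Bias in the first row is 1.2 to 2.8 U/L towards the drug. In the second row it is 8 − 7.6 = 0.4 to 8 − 6.9 = 1.1 U/L against the drug. The sign changes because, when the drug truly lowers enzymes, a common rule removes more placebo patients. That pulls the placebo mean down and shrinks the difference. If equally many, equally large risers left each arm, the effects would roughly cancel.

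**4. Check with a likelihood-based repeated-measures model.** Assumptions: SD 1, AR(1) correlation 0.5 or 0.7, no drug effect, active-arm patients with the largest month-1 rise leaving before month 2, placebo dropout random, 1,000 runs.
- 5 of 50 leaving per arm: complete-case shows a false fall of 0.03 to 0.06 SD, or 0.03 × 25 = 0.75 to 0.06 × 25 = 1.5 U/L. Repeated measures gives about 0.00.
- 10 of 50 leaving on active and 5 of 50 on placebo: false fall 0.07 to 0.12 SD, or 1.75 to 3.0 U/L. Repeated measures is within about 0.01 SD of zero.
- Spread of the estimates: about 0.20 to 0.22 SD for both methods, or 5.0 to 5.5 U/L.

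**5. Bias against standard error.** For the ANCOVA, SE ≈ SD × √(1 − r²) × √(2/45), where r is the correlation between baseline and week 12. With r = 0.8: 25 × 0.6 × 0.211 = 3.2 U/L. With r = 0.6: 25 × 0.8 × 0.211 = 4.2 U/L. Under AR(1) r is lower and the SE larger. The largest bias in step 3, 2.8 U/L, is below even the smallest of these.

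**The case against.** The strongest defence is that baseline-adjusted ANCOVA at one endpoint is a recognised choice for an unpowered secondary outcome with about 10% attrition, and that the bias is small against the noise. The second half stands and limits the weight of the point. It does not show that scheduled data should go unused when using them costs almost nothing in precision.

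The both-measures rule is written for liver fat and reaches the enzymes only through the reference to an analogous analysis. That is an inference, but the natural one, and no other rule is given.

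A reader might infer four stronger things that the documents do not support:

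- **That the bias must favour the drug.** The second simulated mechanism goes the other way, so direction depends on who leaves.
- **That drug-related enzyme rises will drive patients out.** The documents report no such rises and no enzyme-related dropout or stopping rule. The DSMP might contain one. If one assumes that 10% of active patients have a drug-related rise and the largest risers leave, the true difference is about −1.9 U/L and complete-case ANCOVA gives −4.2 to −7.3. An all-visit model still gives −3.3 to −5.0, removing only about 30 to 50% of the bias. That scenario is invented, and the fix leaves at least half of its bias in place.
- **That everyone who stops study drug is excluded.** Exclusion follows from a missing week-12 value. A patient who stops the drug but returns stays in.
- **That the monthly values are thrown away.** They serve safety monitoring. They are only unused in the efficacy comparison.

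**Conclusion.** The point holds as a modest, conditional weakness in a secondary analysis. On the natural reading, up to about 10 of 100 patients could be left out of the AST and ALT test while having usable on-treatment values. If leaving depends on observed enzyme changes, the week-12 estimate can be biased in either direction. At 10% dropout and an assumed SD of 25 U/L, this is about 1 to 3 U/L towards the drug or about 1 U/L against it, below one standard error. Under random dropout it is near zero.

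The text alone supports the exclusion. The size rests entirely on assumed SDs, correlations and dropout mechanisms. An all-visit model was nearly unbiased in these cases because leaving depended only on recorded values.

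**What to change.** In the Secondary Analysis section, take AST and ALT out of the general ANCOVA sentence and specify:

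- a mixed model for repeated measures with treatment, visit, treatment-by-visit, baseline and baseline-by-visit, and an unstructured covariance matrix;
- all scheduled monthly values through week 12, whether or not the patient is still taking study drug;
- all randomised patients with a baseline and at least one post-baseline value;
- the week-12 treatment difference as the tested contrast.

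The words on or off study drug matter. Restricting the model to on-treatment values would discard week-12 readings from patients who stopped but returned, which the current intention-to-treat rule keeps, and would change the quantity being estimated. The value taken one month after therapy lies beyond week 12 and stays out of this model.

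The cost is a few lines of SAP text and slightly more analysis work, with no new data collection. The model relies on data being missing at random. It lessens but does not remove bias if leavers' later enzymes differ from what their earlier values predict, so a short sensitivity analysis would be a sensible companion.
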